We propose to study a total of 175 subjects in three groups. Two groups contain OEF/OIF/OND Veterans (age 18-60) diagnosed with chronic mTBI with persistent PCS (majority due to blast). Participants in these two groups will be matched on age, gender, education, combat exposure, symptom chronicity, and socioeconomic status. Group 1 (mTBI-IASIS group, N=50) contains mTBI Veterans to be blindly assigned to a 6-weeks IASIS treatment with two sessions per week. Group 2 (mTBI sham group, N=50) contains mTBI Veterans to be blindly assigned to a sham treatment for 6 weeks with also two sessions per week. Veterans with mTBI in both Groups 1 and 2 must currently have persistent PCS at least 6 months post injury (i.e., the most recent injury). In addition, PTSD symptoms will be assessed and matched in symptom severity and diagnostic category in the two mTBI groups. Group 3 (control group, N=75): age-, gender-, education-, combat exposure-, and socioeconomically-matched HC Veterans.

The above table and Fig. 10 shows the study flow chart with 16 visits. After consent, Visit 1 for all three groups will include baseline neuropsychological (NP) and mental health assessment (MHA). Then, baseline rs- MEG and MRI scans will be performed in Visit 2 for all participants. The rs-MEG data from the HC group will be used to establish a normative HC database. Next, a re-test rs-MEG exam will be performed in a subset of HC participants (N=25, green dashed line) at Visit

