D.1.2. Exclusion criteria for study participations include: 1) history of other neurological, developmental, or psychiatric disorders (based on the DSM-5 (MINI-7) [86] structured interview), e.g., brain tumor, stroke, epilepsy, Alzheimer's disease, schizophrenia, bipolar disorder, ADHD, or other chronic neurovascular diseases such as hypertension and diabetes; 2) substance or alcohol use disorders according to DSM-5 [87] criteria within the six months prior to the study; 3) history of metabolic or other diseases known to affect the central nervous system (see [88] for similar criteria); 4) Metal objects (e.g., shrapnel or metal fragments) that fail MRI screening, or extensive metal dental hardware (e.g., braces and large metal dentures; fillings are acceptable) or other metal objects in the head, neck, or face areas that cause non-removable artifacts in the MEG data; 5)

Potential subjects will be administered the Beck Depression Inventory (BDI-II) to evaluate level of depressive symptoms, and suicidal ideation; any participant who reports a "2" or "3" on the BDI-II: item 9 (suicidal thoughts or wishes) will also be excluded. However, depression following mTBI or traumatic event of PTSD is common [89]; therefore, in two mTBI groups, we will include and match patients with depression symptoms reported after their injury/event, and will co-vary BDI-II score in data analyses.

D.1.3. Inclusion for the mTBI groups: All symptomatic mTBI patients will be evaluated in a clinical interview to document the nature of the injuries and ongoing PCS. The diagnosis of mTBI patients is based on standard VA/DOD diagnostic criteria. Inclusion in the mTBI patient group requires a TBI that meets the following criteria: 1) a loss of consciousness (LOC) < 30 minutes or transient confusion, disorientation, or impaired consciousness immediately after the trauma; 2) post-traumatic amnesia (PTA) < 24 hours; 3) an initial Glasgow Coma Scale (GCS) [90] between 13-15 (if available). Since the GCS assessment is often not available in theater, Veterans with missing GCS, but who meet other inclusion criteria will also be recruited. Each patient must have at least 3 items of persistent PCS (see below) at the beginning of the study.

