D.4.3. IASIS's immediate effect of slow-wave potentiation -- pre- and post-session rs-MEG changes: To achieve this goal, we will perform three pairs of pre- and post-session rs-MEG exams at the beginning, midpoint, and the end of the IASIS treatment course: in Visit 3 for the 1st IASIS session (S1), Visit 9 for the 7th IASIS session (S7), and Visit 14 for the 12th IASIS session (S12). The post-treatment rs-MEG will be performed within 30 minutes immediately after the treatment session. Two-factor mixed-design repeated measures ANOVA with covariates, equivalent to linear mixed effect model, will be applied for statistical analysis. We will: 1) assess the within-subject significance of the immediate slow-wave potentiation due to IASIS session by comparing the voxel-wise Z-score and total abnormal MEG Z-scores between pre- and postsession exams; and 2) assess the between-group treatment effect by comparing IASIS with Sham. The total abnormal MEG Z-score is calculated by summing up the Z-score from all voxels that showed statistically significant slow-wave generation. The dependent variables at both time points are either voxel-wise Z-scores or total abnormal MEG Z-scores, and the predictors are time (pre- and post-session), group (IASIS versus Sham), and their interaction. Veterans receiving IASIS treatment but not sham are expected to show significantly increase rs-MEG slow-wave generation in post-session rs-MEG exam immediately after the treatment session (Hypothesis 2). The preliminary result in C.5 (Fig. 5) supports this hypothesis.

D.4.4. Ultimate slow-wave reduction following the IASIS treatment course -- pre- and post-treatment rs-MEG exams: Participants in mTBI-IASIS group will participate in the 6-week IASIS treatment, whereas those in mTBI-Sham group will participate in a sham treatment for the same time period. To assess the ultimate effect of the IASIS treatment course, the 1-week post-

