treatment follow-up rs-MEG in Visit 15 will be compared with the baseline rs-MEG in Visit 2 (Fig. 10). The focus of our analyses are the pre- and post-IASIS change in the abnormal MEG slow-wave generation for both voxel-wise Z-score maps and the total abnormal MEG Z-scores. Two-factor mixed-design repeated measures ANOVA with covariates will be used to: 1) assess the within-subject treatment effect by comparing the voxel-wise Z-score and total abnormal MEG Z-scores between pre- and post-treatment exams; and 2) to assess the between-group treatment effect by comparing IASIS with Sham. Participants receiving IASIS treatment, but not sham, are expected to show significantly reduction in abnormal rs-MEG slow-wave generation in post- over pre-IASIS exams (Hypothesis 3). Preliminary result in C.6.2 and C.6.3 (Figs. 6B and 7) supports this hypothesis.

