We will study clinical symptom changes due to IASIS treatment. In both mTBI groups, RPQ and NSI will be used to assess PCS and their changes due to IASIS/Sham treatment. Since PCS will be assessed in all visits, we can trace the PCS change across the entire treatment course. Of course, the most important comparison will be the PCS between 1-week post-treatment follow-up (Visit 15) and the baseline (Visit 2) exams. Again, two-factor mixed-design repeated measures ANOVA with covariates will be used to: assess the within-subject significance of the PCS changes between pre- and post-treatment exams; and 2) to assess the between-group treatment effect by comparing IASIS with Sham. The dependent variables at both time points are PCS scores, and the predictors are time (pre- and post-treatment), group (IASIS versus Sham), and their interaction. We predict that compared with the sham group, mTBI Veterans received IASIS treatment will show significantly greater decreases in PCS symptoms between baseline and post-treatment assessments (Hypothesis 4). The preliminary result in C.6.1 (Fig. 6A) supports this hypothesis.

Besides RPQ and NSI, we will use the same statistical approach to examine IASIS-related changes in additional symptom measures: CAPS-5 and PCL-5 for PTSD symptoms, PSQI for sleep problems, and MGPQ for pain. Since brain injury increases the likelihood of both PCS and PTSD, we hypothesize that by treating the mTBI aspect using IASIS in Veterans, PCS will improve, and that PTSD symptoms will be reduced as well (Hypothesis 5, C.6.1), consistent with a model in which TBI impairs functioning of prefrontocortical and networked systems that are believed to be integral for inhibiting fear responses and promoting fear extinction [26,79]. False discovery rate (FDR) will be used to correct family-wise error [85].

D.6 Correlating IASIS Related Changes in MEG with Symptoms and Neuropsychological Exams (Aim 3)

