Covariate variables to be included in above statistical analysis: Age, gender, education, combat exposure (DRRI-2), socioeconomics, OSU TBI-ID for lifetime history of TBI, ASSIST and AUDIT for alcohol and substance uses, and order of mTBI to PTSD will be added as covariates in the linear regression and ANOVA analyses in Sections D.4 - D.6. However, since these variables will be matched during our group assignment, we do not predict they will have major impact to the results of statistical analyses.

Exploratory studies: We will add 10 minutes rs-fMRI in Visit 2 to our existing MRI acquisition on a 3T system in the two mTBI groups, and use the data for exploratory FC analyses of the relationship between rsfMRI and rs-MEG using the approach described in [14]. We will also add an N-back MEG task in Visits 2 and 15 for exploratory analyses of changes in working memory function due to IASIS treatment. We have previously found that changes in rs-MEG neural patterns are highly associated with the working memory performance of the N-back MEG task [110].

D.8 Description and Justifications of Sampling Plan, Power Analysis, and Time Table

For assessing the specificity (1- false-positive rate) of the MEG slow-wave measures on a single-subject basis, the number of HC subjects in the normative database has to be sufficiently large. N=75 will allow us to reliably assess the normative datasets from HC participants. By choosing K=3 in the K-fold cross-validation approach, 2/3 (N=50) will be used to construct the normative database and the remaining 1/3 (N=25) to test the specificity, with reliable performance.

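### The group-by-time test planned for Hypotheses 3 to 5 is a valid change-score comparison, but it leaves the baseline outcome unused as a covariate, and the D.7 covariate list omits the BDI-II score promised elsewhere

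*Combined protocol and SAP*

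**What the plan says.** **Model.** D.5 compares PCS scores at Visit 15 with Visit 2. The scores at both visits are the dependent variable, and "the predictors are time (pre- and post-treatment), group (IASIS versus Sham), and their interaction". The same approach is extended to CAPS-5 and PCL-5 (Hypothesis 5). For Hypothesis 3, D.4.4 says "Two-factor mixed-design repeated measures ANOVA with covariates will be used to" compare pre- and post-treatment MEG and IASIS with sham. It does not list the predictors again, so the reading for Hypothesis 3 rests on the shared model name and on the terms given in D.5 and, for the session-level analysis, in D.4.3 ("the predictors are time (pre- and post-session), group (IASIS versus Sham), and their interaction").

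**Covariates.** D.7 gives the list for D.4 to D.6: age, gender, education, combat exposure (DRRI-2), socioeconomics, OSU TBI-ID, ASSIST, AUDIT, and the order of mTBI and PTSD. It expects little effect from them "since these variables will be matched during our group assignment". No baseline outcome appears, and neither does BDI-II. Yet D.1.2 and the exclusion criteria in Section 10 both say that the study "will co-vary BDI-II score in data analyses".

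**Matching.** Under D.1.1 the two mTBI groups "will be matched on age, gender, education, combat exposure, symptom chronicity, and socioeconomic status". In addition, "PTSD symptoms will be assessed and matched in symptom severity and diagnostic category in the two mTBI groups". D.1.2 adds matching on depression symptoms. PCS severity and MEG slow-wave level are not named as matching factors.

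**Allocation.** D.4.2 has a staff research associate assign participants to arms and describes no random sequence.

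**The concern.** The trial collects a baseline value of every outcome in Hypotheses 3 to 5, but the planned model uses it only as half of a difference. Unless baseline and follow-up are very highly correlated, a change score carries more noise than a follow-up score adjusted for baseline, so the interval for the treatment effect is wider than it need be.

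For Hypotheses 3 and 4 the baseline outcome is neither matched nor adjusted. Entry under D.1.3 depends on symptoms ("Each patient must have at least 3 items of persistent PCS (see below) at the beginning of the study"), so some fall without treatment is plausible. If one arm happens to start higher, a change score credits part of its larger fall to that arm.

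The BDI-II mismatch is a separate matter. If it stays, the analyst must choose between D.1.2 with Section 10 and D.7, possibly after seeing results.

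**Working it through.** **1. The planned test is a change-score test.** With two time points and complete pairs, the group-by-time coefficient equals the difference between arms in mean change. On one simulated data set (50 per arm) the mixed model and the difference in mean change both gave -0.4226 with |t| = 2.160. Baseline-adjusted ANCOVA on the same data gave -0.462 with |t| = 2.648. Covariates that do not vary over time, entered only as main effects, leave the group-by-time estimate unchanged, and D.5 names no covariate-by-time term.

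**2. Inputs.** From D.8: 50 per arm (N = 100), two-tailed alpha 0.01, f = 0.38 (RPQ), 0.32 (PCL) and 0.45 (Hypothesis 3), with stated power above 0.95, 0.85 and 0.98. D.8 names G*Power but gives no routine, correlation or scale of f for these hypotheses. The pre-post correlation rho is my assumption, 0.3 to 0.7. The nearest figure in the protocol is the expected MEG test-retest ICC of at least 0.75, which covers consecutive exams and not the treatment course.

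**3. The plan's own figures.** Power is from the noncentral F. With the repeated-measures between-factors formula, lambda = 2f²N/(1+rho), and rho = 0.5:
- RPQ: 2 × 0.1444 × 100/1.5 = 19.25, power 0.959
- PCL: 2 × 0.1024 × 100/1.5 = 13.65, power 0.855
- Hypothesis 3: 2 × 0.2025 × 100/1.5 = 27.0, power 0.994

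These agree with the stated bounds, but that formula tests the group main effect, not the interaction. With G*Power's interaction formula, lambda = 2f²N/(1-rho), power at rho = 0 is already 0.997 (RPQ) and 0.969 (PCL), and it rises with rho. The agreement therefore does not show which routine was used.

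**4. Gain from the baseline covariate.** For a raw SD of 1, the variance is 2(1-rho) for a change score and 1-rho² for ANCOVA. The ratio is (1+rho)/2 = 0.65, 0.75 and 0.85 at rho 0.3, 0.5 and 0.7. The square roots are 0.806, 0.866 and 0.922, so the interval is about 19%, 13% and 8% narrower. With f per SD of change, lambda is f²N for the change score (df 98) and 2f²N/(1+rho) for ANCOVA (df 97). Power at alpha 0.01:

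| Outcome | Change score | ANCOVA, rho 0.3 | rho 0.5 | rho 0.7 |
|---|---|---|---|---|
| RPQ, f 0.38 | 0.877 | 0.980 | 0.959 | 0.930 |
| PCL, f 0.32 | 0.716 | 0.907 | 0.855 | 0.798 |
| Hypothesis 3, f 0.45 | 0.968 | 0.998 | 0.994 | 0.987 |

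**5. Cost of uninformative covariates.** The nine D.7 items, counting DRRI-2 as the two scales in D.1.5, plus BDI-II make 11; the baseline outcome makes 12. If the 11 explain nothing, lambda is multiplied by 1 - 12/99 = 0.879 and df is 86. At rho 0.5 power becomes 0.928 (RPQ) and 0.794 (PCL). At rho 0.75 it is 0.877, 0.715 and 0.968 (Hypothesis 3), the same as the unadjusted change score to within 0.001.

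**6. Baseline differences.** Simulated with no treatment effect, rho 0.5 and 50 per arm. The figures are the share of results significant in favour of IASIS at two-sided 0.05 (40,000 runs each):

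| Situation | Change score | ANCOVA |
|---|---|---|
| Random allocation, no condition on baseline | 2.4% | 2.4% |
| Chance imbalance fixed at 0.4 SD, IASIS higher | 13% | 2.6% |
| Stable group difference of 0.4 SD, IASIS lower, no change in either arm | 2.4% | 20% |

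The standard error of the baseline difference is sqrt(2/50) = 0.2 SD, so 0.4 SD is two standard errors. A chance imbalance shifts the change-score contrast by (1-rho) times the imbalance. For 0.2 SD that is 0.14, 0.10 and 0.06 SD at rho 0.3, 0.5 and 0.7.

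**The case against.** A mixed ANOVA on two time points is a standard, pre-specified analysis. A reader might infer from the fixed-imbalance row that the planned test is biased or invalid. The documents do not support that. Under random allocation both tests hold their nominal level, and a chance imbalance of two standard errors in a given direction arises only about 2% of the time.

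Nor does ANCOVA remove baseline distortion in general. If the arms differ for a stable reason, ANCOVA is the model that misleads, and D.4.2 leaves that possibility open because it describes assignment by staff without stating randomisation.

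The precision gain is also limited. Hypothesis 3 has little room to improve. PTSD severity is matched for Hypothesis 5, so baseline imbalance matters less there. The larger gains for RPQ and PCL depend on reading f per SD of change. All of this stands.

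On BDI-II, D.7 does not say that its list is exhaustive, and the three places can be read together. That is fair, but D.7 is where an analyst will look for the covariates, so the texts should agree.

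Finally, recruitment has closed (Section 11.1) and visits stopped on 09/30/2022 (Section 20). Replacing a pre-specified model with a more powerful one at this stage would add analytic flexibility. This is a good reason to keep the planned test in full view.

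**Conclusion.** The planned test for Hypotheses 4 and 5, and for Hypothesis 3 by the same model name, is valid but does not use the baseline outcome as a covariate. If f is per SD of change and rho is 0.3 to 0.7, adjustment adds 0.05 to 0.10 to RPQ power and 0.08 to 0.19 to PCL power at alpha 0.01. For Hypothesis 3 it adds 0.02 to 0.03. The gain is cancelled near rho 0.75 if the other 11 covariates are uninformative, and it is immaterial if f is G*Power's interaction f. The documents give no pre-post correlation, so the true gain is unknown.

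A reader might also infer that the stated power is wrong. It is not shown to be false: D.8 does not name the routine, the correlation or the scale of f, and the stated figures can be reached under more than one reading.

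Which model is safer against a baseline difference depends on how participants were allocated, which the protocol does not settle. The BDI-II inconsistency needs no assumption: D.1.2 and Section 10 promise a covariate that D.7 does not list.

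**What to change.** 1. For Hypotheses 3 to 5, analyse the Visit 15 outcome by arm, adjusted for its own baseline, BDI-II and the D.7 covariates. Name each baseline: Visit 2 for MEG and PCS, Visit 1 for PCL-5, and the pre-treatment past-week CAPS-5.
2. Report the planned group-by-time result beside it with equal prominence, with baseline means by arm. State whether allocation was random. If it was not, or if the two models disagree, call the result not robust.
3. Add BDI-II to the D.7 list so that it agrees with D.1.2 and Section 10.
4. Record this in a dated amendment before any unblinded outcome analysis. If the codes are already open, say so and report both models.

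The cost is analysis wording only, with no new data. Some precision is lost if the added covariates explain little, and a model is added after data collection, which is why the planned test stays at equal rank.

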Correlating IASIS-related changes in MEG slow-wave source imaging and PCS in mTBI: Correlation analyses will be performed to examine the neuronal correlates of changes in MEG slow-wave generation and PCS scores in Veterans with mTBI in both IASIS and Sham groups. Specifically, we will correlate the changes in the total abnormal MEG Z-scores as well as voxel-wise Z-score MEG source imaging measures with changes in PCS due to IASIS treatment, by comparing PCS scores from post-treatment follow-up (Visit 15) with the baseline (Visit 2) exams. We predict that reduction in MEG slow-wave generation will correlate with reduced total PCS score as well as specific symptom scores (e.g., sleep disturbance, post-traumatic headache, photophobia, and memory problem symptoms) (Hypothesis 6). The voxel-wise analysis may provide important spatial information of the slow-wave generation related to each PCS category. Linear regression analyses will be performed for the correlation analysis, and FDR will be used to control family-wise error [85] using correct $q < .05$. We predict that in mTBI-IASIS group, but on

in the sham group, reduction in MEG slow-wave generation will correlate with reduced symptoms. Preliminary data presented in Section C.6.2 and Fig. 6C support this hypothesis.

Correlating IASIS-related changes in MEG slow-wave source imaging and cognitive functions in mTBI: We will study the relationship between changes in MEG slow-wave generation with those in neuropsychological exam scores between post-IASIS (Visit 15) and baseline exams (Visit 2). For neuropsychological tests that differentiate HC and mTBI groups, we will perform linear regression analysis, where treatment-related changes

in neuropsychological test scores are used to predict the changes in MEG measures including voxel-wise slowwave Z-score (FDR corrected for family-wise error) and the total abnormal MEG Z-scores. We also predict that in mTBI-IASIS group, but not in the sham group, reduction in MEG slow-wave generation will correlate with improvement in the different cognitive domains that govern functioning.

D.7 Examining the effects of Covariate Variables on IASIS treatment and Exploratory Analyses in mTBI

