Power analysis: We don't expect that one set of sample sizes will meet the needs of all 3 aims and 6 hypotheses equally well. Hence, for a proposed set of sample sizes, some hypotheses may be overpowered whereas the others may be adequately powered. We used G*Power (University of Dusseldorf) for the power analysis. The power analyses below show that the N=50 in each of the two mTBI groups (i.e., mTBI-IASIS and mTBI-Sham) provides a good balance for all the hypotheses. For Hypothesis 1, our voxel-wise MEG slowwave source imaging is expected to show substantially higher sensitivity in detecting in mTBI groups than conventional MRI. Based on our preliminary data using McNemar's test in C.2, we expect a large effective size (odds ratio > 50). At two-tailed, $\alpha=0.01$, N=50 in each of the mTBI groups, the estimated power is > 0.98. We also predict high test-retest reliability of MEG slow-wave source imaging measures in N=100 Veterans (50 in each group) that will have two consecutive MEG exams (Visits 2 and 3). Based on our preliminary data in C.4, high level of test-retest reliability (i.e., ICCs ≥ 0.75) is expected in our rs-MEG slow-wave source imaging. In Hypothesis 2, we predict that IASIS treatment will enhance neural healing by initially potentiating slow-wave generation immediately after each treatment session. In Hypothesis 3, we expect that in Veterans in mTBI-IASIS group, but not in mTBI-Sham group, MEG source imaging (voxel-wise and total Z-score) will ultimately show a significant decrease in abnormal slow-waves between pre- and post-treatment exams. Based on preliminary data in C.5 and C.6 (Figs. 6B and 7), for Hypotheses 2 and 3, we expect large effect size (Cohen's $f>0.45$). At two-tailed, $\alpha=0.01$, N=50 in each of the mTBI groups, the estimated power is > 0.98. In Hypotheses 4 and 5, we predict that, compared with the sham group, mTBI participants in the IASIS treatment group will show significantly larger decreases in PCS and PTSD symptoms between baseline and post-treatment assessments. Based on pilot data in C.6 and information from [68], we expect medium-to-large effective size for total the RPQ (Cohen's $f>0.38$) and medium-to-large effective size for PCL (Cohen's $f>0.32$). At two-tailed, $\alpha=0.01$, N=50 in each of the mTBI groups, the estimated power is > 0.95 for total RPQ score, and power > 0.85 for PCL. We will also have power > 0.88 for 5 individual PCS scores (e.g., PSQI for sleep problems, MGPQ for pain, etc.) with the conservative Bonferroni correction. For Hypothesis 6, we expect changes in MEG slowwaves will correlate with PCS scores and cognitive deficits in specific domains in mTBI groups due to IASIS. Based on our preliminary data in C.6 and C.7, we expect medium-to-large effect sizes ($|r| \sim 0.4-0.8$). With N=50 in each mTBI group, two-tailed, $\alpha=0.05$, the estimated powers are > 0.85 for changes in MEG slow-wave correlating with total PCS score or one NP variable. The same level of power can be achieved for 5 symptom individual PCS / NP variables at $\alpha=0.05$, in the conservative case of Bonferroni correction, and for more than 5

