1) history of other neurological, developmental, or psychiatric disorders (based on the DSM-5 (MINI-7) [86] structured interview), e.g., brain tumor, stroke, epilepsy, Alzheimer's disease, schizophrenia, bipolar disorder, ADHD, or other chronic neurovascular diseases such as hypertension and diabetes; 2) substance or alcohol use disorders according to DSM-5 [87] criteria within the six months prior to the study; 3) history of metabolic or other diseases known to affect the central nervous system (see [88] for similar criteria); 4) Metal objects (e.g., shrapnel or metal fragments) that fail MRI screening, or extensive metal dental hardware (e.g., braces and large metal dentures; fillings are acceptable) or other metal objects in the head, neck, or face areas that cause non-removable artifacts in the MEG data; 5) Potential subjects will be administered the Beck Depression Inventory (BDI-II) to evaluate level of depressive symptoms, and suicidal ideation; any participant who reports a "2" or "3" on the BDI-II: item 9 (suicidal thoughts or wishes) will also be excluded. However, depression following mTBI or traumatic event of PTSD is common [89]; therefore, in two mTBI groups, we will include and match patients with depression symptoms reported after their injury/event, and will co-vary BDI-II score in data analyses.

Section 10.6 Avoiding coercion of students or employees

10.6) Indicate how coercion of students and/or employees will be avoided:

The fact that someone may be a student or employee is not relevant to participation in the study. These individuals are not targeted for inclusion and their student or employee status will not be recorded in the study. All students or employees must be Veterans to participate.

Section 11 - Recruitment

11) Describe, step-by-step, the plans for recruitment of subjects (or selection of subjects as in record review). This description must include how, when, and where potential subjects are approached as well as procedures

for identifying potential participants (through medical records, physician referral, third-party sources, etc.). Include how selection is equitable. Indicate if vulnerability to coercion may be present and if so plans to ensure voluntary participation.

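### D.6 predicts that slow-wave reduction tracks improvement in IASIS but not in sham, yet no test of whether the relation differs between the arms is planned

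*Combined protocol and SAP*

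**What the plan says.** All references are to the combined protocol and SAP.

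- **D.6, cognition:** "We also predict that in mTBI-IASIS group, but not in the sham group, reduction in MEG slow-wave generation will correlate with improvement" in the cognitive domains.
- **D.6, symptoms:** a parallel sentence covers symptom reduction. Its wording is garbled at the key point ('on' where 'not' seems meant). Read that way, it makes the same prediction.
- **D.6, method:** "Linear regression analyses will be performed for the correlation analysis", and "FDR will be used to control family-wise error". Both arms are to be analysed, but D.6 does not say whether together or separately. For cognition the direction is fixed: changes "in neuropsychological test scores are used to predict the changes in MEG measures", so MEG change is the outcome. For symptoms the direction is left open.
- **D.7:** nine variables "will be added as covariates in the linear regression and ANOVA analyses in Sections D.4 - D.6". Exclusion criterion 5 (D.1.2 and Section 10) adds that the investigators "will co-vary BDI-II score in data analyses".
- **D.8:** with 50 in each mTBI group, two-sided alpha 0.05 and |r| of about 0.4 to 0.8, "the estimated powers are > 0.85 for changes in MEG slow-wave correlating with total PCS score or one NP variable". This is power for one correlation, not for a difference between two.
- **D.4.3 and D.5:** group, time and their interaction are named as predictors, for the MEG scores and the symptom scores respectively.
- **Section 6, Hypothesis 6:** slow-wave reduction will correlate with lower symptom scores and better test scores. Sham is not mentioned.

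**The concern.** The prediction is comparative: a relation in one arm and none in the other. Two readings of the planned regressions are possible, and neither tests it. A single regression over both arms without arm terms gives one common slope. Separate regressions give two p-values, and a significant result beside a non-significant one is not evidence that the two relations differ.

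The group-by-time terms in D.4.3 and D.5 do not fill the gap. They test whether mean change differs by arm, not whether MEG change and clinical change move together differently in each arm.

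At stake is a mechanistic statement. A modest relation common to both arms (for example, people who happen to improve also show less slow-wave activity) could be reported as specific to IASIS because one of two equal correlations missed significance.

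**Working it through.** **Inputs.** From D.8: n = 50 per arm, two-sided alpha 0.05, |r| from 0.4. Assumed: regressions run by arm, a full 50 in each, one variable, no covariates, and the same true r in both arms.

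**Step 1. D.8's own power figure.** Regression t test with fixed predictor: noncentrality = sqrt(n) × r / sqrt(1 − r²) = 7.071 × 0.4 / 0.9165 = 3.086 on 48 df. Power is 0.856, which matches the stated figure of more than 0.85. The exact bivariate-normal calculation gives 0.835, and Fisher z gives Φ(0.4236 × sqrt(47) − 1.96) = 0.828.

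**Step 2. How often equal correlations look arm-specific.** The arms are independent, so P(significant in the predicted direction in IASIS, not significant in sham) = p(1 − p), where p is the power. For small r, p in the second factor counts significance in either direction.

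| True r in both arms | Power p (range over methods) | IASIS only |
|---|---|---|
| 0.2 | 0.29 | 20-21% |
| 0.3 | 0.57-0.59 | 24% |
| 0.4 | 0.828-0.856 | 12-14% |
| 0.5 | 0.964-0.979 | 2-3% |
| 0.6 | 0.997-0.999 | under 0.5% |

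Example at r = 0.4: 0.856 × 0.144 = 0.123, and 0.828 × 0.172 = 0.143. With r = 0 in both arms the rate is about 2.4%. Simulation agrees (13.8% at 0.4, 3.2% at 0.5).

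**Step 3. Sensitivity.** With 40 per arm (assumed), the rates are 18-20% at r = 0.4 and 5-8% at 0.5. At alpha 0.01, which is 0.05/5 and corresponds to D.8's illustration "in the conservative case of Bonferroni correction" for five variables, they are 23% and 8-10% with 50 per arm.

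**Step 4. Which variable should be the predictor in a direct test.** Suppose clinical change = b × MEG change + error, with the same b and the same error SD in both arms. Scale IASIS so that both variables have SD 1 and b = r = 0.4; the error variance is then 0.84. Now let MEG change have half that SD in sham (assumed; the documents give no SDs).

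- Clinical change on MEG change: the slope is 0.40 in both arms.
- MEG change on clinical change: 0.40 in IASIS, but 0.4 × 0.25 / (0.16 × 0.25 + 0.84) = 0.10 / 0.88 = 0.11 in sham.
- Correlation: 0.40 in IASIS, but 0.4 × 0.5 / sqrt(0.88) = 0.21 in sham.

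So with MEG change as outcome, unequal spread alone makes the slopes differ. Simulation of this shared relation (50 per arm, no covariates, heteroscedasticity-robust HC3 errors, nominal 5%) gives these rejection rates when the sham MEG SD is smaller by a factor of 1.5 and 2:

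| Test | IASIS r = 0.4 | IASIS r = 0.6 |
|---|---|---|
| Interaction, MEG change as outcome | 22%, 44% | about 39-40%, 76% |
| Interaction, MEG change as predictor | about 5% | about 5% |
| Fisher z on correlations | 10%, 18% | 18%, 34-36% |

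**Step 5. Power of a direct test.** Fisher z for r against 0: Φ(atanh(r) / sqrt(2/47) − 1.96). At r = 0.4 this is Φ(0.4236/0.2063 − 1.96) = 0.54, and at 0.5 it is Φ(0.5493/0.2063 − 1.96) = 0.76. With ten covariates (nine in D.7 plus BDI-II), sqrt(2/37) replaces sqrt(2/47), giving 0.45 and 0.66. The interaction with MEG change as predictor has about 0.5 and 0.7 without covariates and with equal spread.

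**The case against.** The best reply is that D.6 states an expectation, not a decision rule. Nowhere does it say that significance in one arm only will be taken as proof of a difference. Over most of the range that D.8 expects, the false pattern is rare: by r = 0.5 it is already below the 5% error rate of a direct test. The two sentences also sit in the third aim, outside Hypothesis 6 as worded, and do not touch the efficacy comparisons of Hypotheses 3 to 5. All of this stands, and it limits the weight of the point. It does not remove the gap: a contrast is predicted and nothing planned tests it.

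A reader might infer more in three ways that the documents do not support.

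- That D.7 shows arm is left out of the regressions because its list does not name arm. The same list serves the ANOVAs of D.4 and D.5, where group is explicitly a predictor and is also not listed. The list settles nothing.
- That Hypothesis 6 itself is untestable. It predicts a correlation without a sham contrast, and the planned regressions address that.
- That an IASIS-only result would usually be false. That depends on the true correlations, which the documents do not give by arm. The pilot correlation in C.6.2 (r = 0.84) comes from six IASIS-treated people with no sham arm described.

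**Conclusion.** The point holds in limited form. D.6 predicts an arm-specific relation for cognition and, on the natural reading of a garbled sentence, for symptoms. No section specifies a test of whether the relation differs by arm or says how the arms enter the regressions.

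The size depends on a by-arm analysis, 50 per arm and an equal true correlation. The chance of a spurious IASIS-only result matters when that correlation is about 0.4 or less and is negligible at 0.6 or above. Fewer completers or a stricter alpha would raise it.

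This is a cheap improvement to a secondary mechanistic claim, not a flaw in the efficacy analysis. A direct test would show whether the relation differs by arm; it would not show that slow-wave reduction mediates a treatment effect.

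**What to change.** Add to D.6, for the total abnormal MEG Z-score with each PCS and neuropsychological measure:

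1. Regress symptom or test-score change on MEG change, arm, and arm by MEG change. Keep the planned covariates and FDR control, and let residual variance differ by arm.
2. Use MEG change as the predictor for this contrast in both sets of pairs. Hypothesis 3 expects MEG change to behave differently in the two arms, so its spread may differ too, and step 4 of the working shows what that does when MEG change is the outcome. The planned regressions of MEG change on test-score change can stay for within-arm or pooled estimates.
3. Because D.6 and D.8 speak of correlations, report a Fisher z comparison of the (partial) correlations alongside, with the SD of each change score by arm.
4. Claim an IASIS-specific relation only if the interaction is significant. Otherwise give both within-arm estimates and their difference with confidence intervals, and call the sham contrast descriptive.
5. State whether the Hypothesis 6 correlation is tested pooled or by arm.
6. Label the comparison as added after data collection, since Section 20 records that study visits stopped on 09/30/2022.

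The cost is a few sentences and no new data. The downside is that the arm-specific claim becomes harder to reach: power is only about 0.54 if r is 0.4 in IASIS and 0 in sham, and 0.76 if it is 0.5 against 0 (Fisher z, no covariates), and less with covariates or FDR.
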